Food Additives Effects on EEG Profiles in College Students With ADHD

NCT03342469

Submitted 7/15/2019, Edited 7/23/2020

Protocol

Participants with ADHD and controls without ADHD will be recruited from a mid-Atlantic University through on-campus advertisements and word of mouth. Inclusion criteria are 1) currently enrolled at the university, 2) 18-24 years old, 3) following a stable medication dose and frequency (ADHD medication or otherwise) for at least 3 months. If in the ADHD group, additional inclusion criteria are 1) diagnosed with ADHD by a primary care doctor, psychiatrist, or psychologist and 2) willingness to suspend ADHD medication for 24-48 hours before testing days. Exclusion criteria are 1) seizure disorder, 2) past hospitalization for asthma, or 3) any comorbid disorder requiring an anti-psychotic medication.

The research study was approved by the University's IRB (IRB-2017-151) and written informed consent will be provided by each participant. Baseline assessments for ADHD and control participants included collection of demographic and anthropometric data, completion of cognitive testing using CNS Vital Signs ® (CNSVS) software, completion of the Adult ADHD Self-Report Scale (ASRS), and 4 minutes of eyes closed resting-state EEG recording. To avoid medication effects, ADHD medication use will be suspended for 24-48 hours before testing, as appropriate for the half-life of the medication.

After baseline testing, ADHD participants and a small subset of control participants will complete in-person dietary training to learn how to identify and avoid AFC in the diet. Dietary training will include reviewing the FDA approved AFC names, identifying such names on food labels, reviewing common foods containing AFC and their AFC-free alternatives, and talking through their average diet to identify foods containing AFC. Participants will be given a paper copy of the dietary training and emailed a PDF version.

Participants will avoid AFC in the diet for the remaining 4 weeks of the study: participants followed the diet for 2 weeks before beginning the 2-week crossover challenge. After 2 weeks on the diet, participants will complete an AFC specific Food Frequency Questionnaire (FFQ) to measure dietary compliance and then will be randomized to a double-blind placebo-controlled crossover challenge for 3 days each, of 2 consecutive weeks. The challenge materials are either 225mg of mixed powder AFC (i.e., Red No. 40, Red No. 3, Yellow No. 5, Yellow No. 6, Blue No. 1, Blue No. 2) disguised in chocolate cookies, or placebo chocolate cookies with no AFC.

Chocolate cookies work well for blinding since when these colors are mixed together, they are close to brown in color. The mixture of AFC was chosen to incorporate the colors most often consumed in the diet, and the amount of each AFC used was half of the Estimated Daily Intake (EDI) of a high-consumer, as determined by the FDA. Powdered AFC will be used to avoid any possible confounding effects from propylene glycol or sodium benzoate which are commonly used in liquid food coloring. A 4-day washout period was implemented to avoid carry-over effects. The CNSVS cognitive testing, ASRS, and EEG recordings will be repeated at the end of each 3-day exposure.

Adult ADHD Self-Report Scale (ASRS)

The ASRS-v1.1 is a reliable and valid scale used for assessing ADHD symptoms based on the DSM-IV-TR criteria in the adult population. The ASRS includes 6 questions in Part A that are considered most predictive of adult ADHD and 12 questions in Part B that further probe at specific symptom profiles. Scoring is based on the frequency of symptoms asked in each question, ranging from 0 for “never” to 4 for “very often”, with a higher score indicating a higher likelihood of ADHD. The ASRS is a screener for adult ADHD and asks about symptoms over the last 6 months, however participants were asked to answer questions based on the week leading up to the testing to capture potential short-term effects of AFC. Additionally, ASRS questions were broken up into “inattentive” or “hyperactive” sub-classifications based on CNSVS protocol for adult ADHD testing, resulting in 9 inattentive questions and 9 hyperactive questions, and then these were scored. Thus, each participant will receive an inattentive, hyperactive, and total ASRS score.

CNSVS Cognitive Testing for Attention

CNS Vital Signs ® (CNSVS) software will be used to test simple and complex attention. Simple attention is measured using a Continuous Performance Test (CPT) to analyze the correct response rate and to assess whether the correct responses are more frequent than commission errors. Complex attention is a composite score created from performance on a Stroop task, CPT, and Shifting Attention Task.

Quantitative Electroencephalography (EEG)

Participants will sit in a comfortable chair facing a computer monitor in an air-conditioned, sound attenuated room. Four minutes of eyes-closed resting-state data will be collected at baseline and at the end of each challenge period. Participants will be instructed to remain as still as possible while being relaxed, but awake.

EEG recording will be completed using g.tec equipment (<http://www.gtec.at>). Twenty-five Ag/AgCL g.SCARABEO Z electrodes (16x10x5 mm, 125 cm lead) will be used with an adult size cap (g.GAMMAcap2) according to the International 10-20 System (FP1, FP2, , F3, F4, F5, F6, F7, F8, Fz, AF3, AF4, C3, C4, Cz, T7, T8, , P3, P4, P7, P8, P9, P10, Pz, O1, O2) with the reference on the right earlobe and the ground electrode placed at Fpz. Impedance remained below 5 kOhm for all electrodes. A sampling rate of 256 Hz, input signal filter of 0.5-60 Hz, and a 60 Hz notch filter were applied online.

EEG recordings will be analyzed in EEGLab and The Batch Electroencephalography Automated Processing Platform (BEAPP). In BEAPP, a bandpass filter will be applied (1 Hz-50 Hz). To remove artifacts, Independent Component Analysis (ICA) with multiple artifact rejection algorithm (MARA) will be used. The data will be re-referenced to the average and segmented into 2-second epochs, with time points rejected if more than 0.01% of the epoch was $>150\mu\text{V}$. Power spectral density (PSD) will be calculated using the Fast Fourier Transform (FFT) with a Hanning window. Mean power and relative power will be calculated for delta (1-4 Hz), theta (4-8 Hz), alpha (8-13 Hz), beta (13-30 Hz), and gamma (30-50 Hz) frequency bands. Mean power is the sum of the power values of each frequency band divided by the frequency bandwidth, a

measure similar to absolute power. Relative power is the absolute power of a specific frequency band divided by the absolute total power of all bands. The theta-beta ratio (TBR) will also be calculated. Each band and ratio was then averaged over frontal electrodes (Fp1, Fp2, F3, F4, F5, F6, F7, F8, Fz, AF3, AF4), central electrodes (Cz, C3, C4), and posterior/temporal electrodes (Pz, P3, P4, P7, P8, P9, P10, T7, T8, O1, O2).

Statistical Analysis Plan (SAP)

All data will be analyzed in SPSS ® V25.0. Baseline comparisons between the ADHD and controls for demographic and anthropometric data will be run using Wilcoxon rank sum test for non-normal continuous variables, Student's t-test for normal continuous variables, or Chi-Square test for categorical variables. Baseline comparisons of mean and relative EEG power between groups will be analyzed using Wilcoxon rank sum test. Challenge week analyses for the ADHD and EC group will be run using General Linear Modeling (GLM) with the within-

subjects variable being the challenge week material (AFC/placebo) and the between-subjects variable being the order of challenge materials. GLMs will be run for ASRS scores (inattentive, hyperactive, and total), simple attention measures, complex attention measures, and each frequency band of interest or TBR in the frontal, central, and posterior regions. At least 75% of the EEG data segments will need to be usable after preprocessing for the participant data to be included in the statistical analyses.

Since this is the first pilot study on this topic, a power analysis for sample size was not able to be performed. Therefore, uncorrected p-values will be reported to a significance level of $p=0.05$ to note possible effects of AFC across all measures.

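### The ASRS is rated over a week of which only the last 3 days are cookie days, which pulls the AFC-placebo contrast toward zero

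*Combined protocol and SAP*

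**What the plan says.** - **Recall window (Adult ADHD Self-Report Scale section).** The instrument normally asks about 6 months. Here "participants were asked to answer questions based on the week leading up to the testing to capture potential short-term effects of AFC". Items are scored 0 to 4 by how often a symptom occurs, and give inattentive, hyperactive and total scores.
- **Exposure and testing (Protocol).** Participants enter a "double-blind placebo-controlled crossover challenge for 3 days each, of 2 consecutive weeks". Between the two exposures: "A 4-day washout period was implemented to avoid carry-over effects". On timing: "The CNSVS cognitive testing, ASRS, and EEG recordings will be repeated at the end of each 3-day exposure".
- **Background diet (Protocol).** "Participants will avoid AFC in the diet for the remaining 4 weeks of the study"; the first 2 of those weeks come before the challenge. One compliance check is described, after those 2 weeks and before randomisation, when "participants will complete an AFC specific Food Frequency Questionnaire (FFQ) to measure dietary compliance".
- **Medication (Protocol, inclusion criteria for the ADHD group).** The criterion is "willingness to suspend ADHD medication for 24-48 hours before testing days".
- **Analysis (Statistical Analysis Plan).** Challenge-week GLMs have material (AFC or placebo) as the within-subject factor and order as the between-subject factor. They are run for the three ASRS scores, among other outcomes. There is no sample size calculation. P-values are uncorrected at 0.05, with the aim of flagging possible AFC effects on every measure.

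**The concern.** The rating window is longer than the exposure it is meant to capture. The cookie days are the last 3 days of the rated week. The 4 days before them precede the assigned material, so that material cannot influence them. A frequency rating that mixes exposed and unexposed days moves the AFC and placebo scores closer together, and neither factor in the GLM can undo this.

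The window therefore works against its stated purpose in the three ASRS analyses. CNSVS and EEG are measured at the test session and are not diluted in this way, so the outcomes differ in sensitivity and nothing in the plan warns of it. The specific risk is that a null ASRS result beside a positive EEG or CNSVS result is read as showing no effect on symptoms.

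**Working it through.** **Inputs.** From the Protocol: 3 exposure days per period, 4 washout days, 2 weeks of avoidance diet before period 1, and the ASRS at the end of each exposure. From the ASRS section: recall over a week, read literally as 7 days. From the SAP: alpha 0.05 (two-sided assumed, as sidedness is not stated). The documents give no sample size, SD, effect size or recall weights, so there is no figure in the plan to reproduce.

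**Day count.** Number the days from the first cookie day: exposure on days 1-3, washout on days 4-7, exposure on days 8-10.
- Period 1: the 7 days ending with day 3 hold 3 cookie days and 7 - 3 = 4 diet days.
- Period 2: the 7 days ending with day 10 are days 4-10, that is 4 washout days and 3 cookie days.

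**Contrast.** Let δ be the AFC-placebo difference on exposed days and w the total weight a rating puts on the 3 cookie days. Without carry-over the other days contribute no difference, so the expected contrast is w × δ. Equal day weights give w = 3/7 = 0.43. The values 0.6 and 0.8 are assumed recency weights, and w = 1 is the no-loss case.

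**Precision relative to a 3-day window**, under two assumed noise models:
- A, noise does not depend on window length: r = w.
- B, daily noise is independent: r = w × √[(1/3) / (w²/3 + (1-w)²/4)]. At w = 3/7 the denominator is 3/49 + 4/49 = 1/7, so r = 3/7 × √(7/3) = 0.655.

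The sample size multiplier is 1/r². Where a 3-day window would give 80% power, the 7-day window gives Φ(2.80r - 1.96). The 80% is a reference point only; the plan does not claim it.

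| w | Contrast kept | r, A / B | N multiplier, A / B | Power, A / B |
|---|---|---|---|---|
| 3/7 | 43% | 0.429 / 0.655 | 5.44 / 2.33 | 22% / 45% |
| 0.6 | 60% | 0.600 / 0.866 | 2.78 / 1.33 | 39% / 68% |
| 0.8 | 80% | 0.800 / 0.977 | 1.56 / 1.05 | 61% / 78% |
| 1 | 100% | 1 / 1 | 1.00 / 1.00 | 80% / 80% |

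**Carry-over.** Suppose a fraction c of δ persists through the washout, with balanced orders and equal day weights. The share kept is [3/7 + (3/7 - 4c/7)]/2 = 3/7 - 2c/7. This is 0.36 at c = 0.25 and 0.29 at c = 0.5. A full rebound of opposite sign (c = -1) gives 0.71, still below 1.

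**Counting the test day.** If testing falls on the third cookie day and that day is not rated, each window holds 2 of its own cookie days, and the period 2 window also takes in one period 1 cookie day. With balanced orders and equal weights the share is [(2/7 - 1/7) + 2/7]/2 = 3/14 = 0.21.

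**Medication suspension.** With m = 1 or 2 days off medication, the share of the window is 33% or 67% of 3 days, against 14% or 29% of 7 days. These days fall inside the 3 cookie days and are the same under both materials. With equal day weights, the 7-day to 3-day contrast ratio is (m/7)/(m/3) = 3/7 if AFC acts only on off-medication days, and ((3-m)/7)/((3-m)/3) = 3/7 if it acts only on on-medication days. The suspension does not change the dilution.

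**The case against.** The investigators saw the recall problem and deliberately cut the window from 6 months to a week. Going to 3 days is a further step on the same trade-off, and nothing in the documents shows that a 3-day ASRS performs better. The size of the loss may be nil: recency could put nearly all the weight on the cookie days, and with w = 0.8 and independent daily noise power is 78% against 80%. The linear model is a simplification for a bounded 0-4 scale, and a 3-day window that is largely off medication could sit nearer the ceiling. The study is an unsized pilot in which any null is weak evidence, and the plan nowhere says it will read a null ASRS as no effect. The past tense in the ASRS section suggests the ratings may already exist.

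Most of this stands as a limit on size. It does not change the direction: a week is closer to the exposure than 6 months, but still more than half of it is unexposed. Instructing participants to rate the week and then relying on them to discount 4 of its days is not a design safeguard. Carry-over in the direction of the effect, or leaving out the test day, shrinks the contrast further, so 43% is not a lower bound. The possible ceiling effect is a genuine unknown. The absence of an FFQ check during the washout adds nothing to the dilution argument; it means only that those days are not confirmed to be AFC-free.

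**Conclusion.** The concern holds. On the protocol's own schedule, 4 of the 7 rated days in each period precede that period's cookies, and any weight on them biases the three ASRS contrasts toward zero. High confidence attaches to the direction only. The loss runs from none (w = 1) to large (57% of the effect at equal day weights, more with carry-over or an uncounted test day). The figures rest on assumed recall weights, a linear rating and one of two noise models; the carry-over and test-day cases also assume balanced orders. With no true effect there is no bias, so the type I error rate is not inflated. What is at stake is a missed or understated symptom effect in a study that sets out to look for signals.

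**What to change.** For the two challenge-week administrations, change the ASRS instruction to ask about *the last 3 days*. Word it identically in both periods and do not mention cookies or AFC, since participants have had "in-person dietary training to learn how to identify and avoid AFC in the diet" and a pointed instruction could prompt expectations. The baseline form can stay as it is: the challenge GLMs compare AFC with placebo only, and the SAP plans no baseline-to-challenge ASRS comparison.

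If the ratings are already collected, state in the SAP and the report that 4 of the 7 rated days lay outside the exposure. State also that a null ASRS result, especially beside a positive EEG or CNSVS result, will not be read as absence of a symptom effect.

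The cost is one line of instruction, or a short limitation statement. The downsides of the 3-day wording are:
- It may be noisier. It loses its advantage if its SD exceeds that of the 7-day rating by a factor of 1/w: 2.33, 1.67 or 1.25 at w = 3/7, 0.6 or 0.8. At w = 1 there is no advantage to lose. The documents give no reliability figure to settle this.
- It departs further from the instrument's 6-month window.
- It gives more weight to the days off medication, equally under both materials.
- Challenge scores no longer share a recall window with baseline.

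### Is it a fault that the challenge-week EEG models do not say whether mean or relative power is tested?

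*Combined protocol and SAP*

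**What the plan says.** The protocol section Quantitative Electroencephalography (EEG) defines two measures. It states "Mean power and relative power will be calculated for delta (1-4 Hz), theta (4-8 Hz), alpha (8-13 Hz), beta (13-30 Hz" and, to complete the list, gamma (30-50 Hz). The definitions are "Mean power is the sum of the power values of each frequency band divided by the frequency bandwidth" and "Relative power is the absolute power of a specific frequency band divided by the absolute total power of all bands". A third quantity follows: "The theta-beta ratio (TBR) will also be calculated". All the bands and the ratio are then averaged within three regions (frontal, central, posterior/temporal).

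The Statistical Analysis Plan (SAP) names both measures at baseline: "Baseline comparisons of mean and relative EEG power between groups will be analyzed using Wilcoxon rank sum test". For the challenge weeks it specifies a general linear model with material (AFC or placebo) within subjects and order between subjects, applied to the ASRS and attention outcomes and to "each frequency band of interest or TBR in the frontal, central, and posterior regions". No transformation is mentioned anywhere.

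The SAP closes by saying that, as a first pilot, "a power analysis for sample size was not able to be performed", and that "uncorrected p-values will be reported to a significance level of" 0.05. The stated purpose is to flag possible effects on every measure.

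**The concern.** The baseline sentence names mean and relative power; the challenge-week clause, shortly after it, names neither. It also refers to bands of interest without listing them, and does not say which power feeds the theta-beta ratio (TBR).

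The two measures answer different questions. A proportional rise in every band shows in mean power and cancels in relative power. A rise in alpha alone leaves the other bands' mean power where it was but lowers their relative power; a fall in alpha raises it. A reported theta effect could therefore mean two different things.

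Two consequences would matter. With uncorrected p-values, a reader needs the number of tests to weigh a result below 0.05, and the text appears to allow two counts. And if the measure or scale were left open until results were seen, the error rate per reported test would rise above 5%.

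**Working it through.** The documents give no sample size, power, effect size or SD for these outcomes, so there is no planned figure to reproduce.

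**1. Number of tests per group.** Inputs from the documents: 5 bands, 3 regions, 1 ratio, 2 measures, 0.05 per test.

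| Reading | EEG tests | Expected false positives, no effect | Chance of at least one, if independent |
|---|---|---|---|
| One measure | 5 × 3 + 3 = 18 | 18 × 0.05 = 0.90 | 1 − 0.95^18 = 0.60 |
| Both measures | 5 × 2 × 3 + 3 = 33 | 33 × 0.05 = 1.65 | 1 − 0.95^33 = 0.82 |

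Independence is only illustrative, since bands and regions are correlated. Adding the three ASRS scores and at least two attention outcomes gives 23 or 38 tests.

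**2. Which reading the text supports.** The regional averaging step refers to each band without naming a measure. It must cover both, because no other averaging step is given and the baseline analysis compares both. The challenge-week clause uses the same shorthand (each band or TBR, by region). The closing sentence extends the uncorrected reporting to all measures. Together these point to 33 tests. As no transformation is given, the defined quantities are themselves the outcomes.

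**3. Source of TBR.** Write T and B for absolute theta and beta power. From mean power the ratio is (T/4)/(B/17) = (17/4) × T/B = 4.25 × T/B. From relative power the total cancels and the ratio is T/B. A constant factor does not change the p-value, and it carries through averaging over electrodes. Only the reported level differs.

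**4. How alpha alone moves the others.** If alpha is a share a of total power and rises 20%, relative power in every other band changes by 1/(1 + 0.2a) − 1. For assumed shares of 0.20, 0.35 and 0.60 this is −3.8%, −6.5% and −10.7%. For a 20% fall it is 1/(1 − 0.2a) − 1, or +4.2%, +7.5% and +13.6%. With both measures reported, the reader can see this: relative theta moves while mean theta does not.

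**5. Error rate per test.** The two-period model with order was simulated for one band in one region. Assumptions: n = 10, 20 or 30; lognormal power; between-person log SD 0.6 with within-person 0.2, or 0.8 with 0.3; two-sided test; 4,000 runs per setting; no true effect.

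- Each choice fixed alone (mean raw, mean log, relative raw, relative logit): 3.0% to 5.5%.
- Either raw measure, whichever is significant: (p1 + p2 + share of runs in which they disagree)/2. At n = 20 with the smaller SDs this is (0.049 + 0.051 + 0.080)/2 = 0.090. Over all settings it runs from 6.6% to 9.0%.
- Any of the four: 9.8% to 12.6%.

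The inflation comes entirely from selection. With both raw measures reported in full, each test stays between 3.0% and 5.1%.

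**The case for a change.** The strongest case for a change is that the both-measures reading is an inference. The baseline sentence names the measures, so their absence from the model clause could signal a different intention. If both are meant, one word would say so, at no cost in data or power. Uncorrected p-values make the count more important, not less. The choice can also alter a finding: with an assumed theta effect of 0.15 log units and n = 20, the two raw measures reached different verdicts in 32% to 38% of simulated trials.

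The omission stands, and so do the two counts. The rest does not carry a change. The disagreement between measures reflects their definitions and argues for reporting both, which is where the text already points. The 7% to 13% error rates need a choice made after seeing results, and nothing in the plan proposes one. On scale, neither raw nor log can be called better from these documents, and the raw-scale model does not exceed its nominal error by more than simulation noise. The source of TBR leaves its p-values untouched. The document was edited in July 2020 and is partly in the past tense, so a sentence added now might not count as prospective in any case.

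**Conclusion.** The challenge-week clause is less explicit than the baseline sentence, but an analyst following the plan would fill the gap sensibly: mean and relative power, all five bands and TBR, three regions, untransformed. That is 33 EEG tests per group, with 1.65 expected to fall below 0.05 by chance; if only one measure were meant, 18 and 0.90. Both counts follow from the documents' own lists.

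No estimate is invalid on either reading, and no particular measure or scale can be recommended over another. A results table that labels each row by measure, band and region shows the number of tests without any amendment. The conclusion rests on the both-measures reading, which is strongly suggested but not printed, and on results being reported across all measures as the SAP says. The simulated error rates depend on assumed sample sizes and variances; the conclusion needs from them only that a test fixed in advance stays near 5%.
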